#### 10.1.2. Study Design Considerations

This is a longitudinal study in subjects with COPD and controls. The follow-up period is 2.5 years with scheduled clinic visits at study entry, 6 months, 18 months, and 30 months.

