where  $\hat{\sigma}_p^2 = \hat{\sigma}_\beta^2 + 12(P - 1)\hat{\sigma}^2 / [D^2 P(P + 1)]$ ,  $r = N_2/N_1$ , and  $N_1$  and  $N_2$  are the sample sizes associated with each of the two groups.

In this study, it is planned to collect  $P=4$  measurements of  $FEV_1$  over  $D=2.5$  years. One of interest is an estimate of the rate of decline in  $FEV_1$  between subjects GOLD I and II.

Under the above assumptions with 95% confidence and a 25% drop out, the following table gives sample sizes necessary to attain the levels of precision of Gold I vs. Gold II comparison.

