**Table 2      Sample size for Gold I vs. Gold II under given precision**

| Interested comparison             | Precision*
(ml/yr) | Subgroup | Completers | Total sample size
including 25%
drop out |
|-----------------------------------|-----------------------|----------|------------|--|
| Gold I vs. Gold II
$r = 1 : 1$ | 15                    | Gold I   | 525        | 700  |
|                                   |                       | Gold II  | 525        | 700  |

\*: half width of a 95% confidence interval

Based on the total completed  $N = 1275$  COPD subjects, a 95% two-sided confidence interval for the rate of decline in  $FEV_1$  of all COPD subjects will have a total width of

$$W = 2 \times Z_{\alpha/2} \times \hat{\sigma}_p / \sqrt{N} = 2 \times 1.96 \times 125.1 / \sqrt{1275} = 13.7 \text{ ml/year}$$

$$\text{where } \hat{\sigma}_p = \sqrt{\hat{\sigma}_\beta^2 + 12(P - 1)\hat{\sigma}^2 / [D^2 P(P + 1)]} = 125.1$$

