## 4. ANALYSIS POPULATIONS

**Table 2. Summary of Study Populations**

Population	Definition / Criteria	Analyses Evaluated
Full population	The Full Population will consist of all subjects who are enrolled in the study and attend Visit 1.	
 
• Disease Progression Analyses
 
• Phenotypic Analyses
 
• Treatment Pattern and Healthcare Resource Utilization/Cost
 
• Safety Analyses
 

Population	Definition / Criteria	Analyses Evaluated
Sub-cohort population	Subjects who are enrolled in the Biomarker & Digital sub-cohort and who provided a least one additional sub-cohort assessment.	
 
• Disease Progression Analyses
 
• Phenotypic Analyses
 
• Treatment Pattern and Healthcare Resource Utilization/Cost
 
• HRCT analysis
 

Completer Population	The Completer Population will consist of all subjects in the Full Population who complete all scheduled clinic visits over 2.5 years.	
 
• Disease Progression Analyses
 
• Phenotypic Analyses
 
• Treatment Pattern and Healthcare Resource Utilization/Cost
 

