### Model specification

- Logistic regression with binary endpoint
- Response variable:
- moderate exacerbation in the 18 months period vs exacerbation free for 18 months in the full population
  - severe exacerbation vs exacerbation free or only moderate exacerbation for 18 months in the full population
  - moderate or severe exacerbation vs exacerbation free for 18 months in the full population
- Predictors/ covariates

- **Continuous variables:** age, Number of pack-years, Total SGRQ score, FEV1 % pred (post), FVC % pred (post), mMRC, CAT, Hemoglobin and remove (some of) aforementioned covariate(s) or add other covariate(s) if needed.
- **Categorical variables:** Gender, Smoking status (former vs never, current vs never), Education level (high school vs less high, above school vs less high), Type of hospital, Household income (low income  $\leq 80000$  vs high income  $> 80000$ ), GOLD grade (II vs I, III vs I, IV vs I), Neutrophil/lymphocyte ratio (low  $< 5$ , high  $\geq 5$ ), Eosinophils (low  $< 300$ , high  $\geq 300$ ), CRP (low  $\leq 3$ , high  $> 30$ ), Fibrinogen (low  $< 400$  high  $\geq 400$ ), Asthma diagnosed before age 40 (either in Medical History or Childhood Respiratory Asthma is diagnosed as yes, then labelled as yes), Moderate exacerbations in one year (yes or no), Severe exacerbations in one year (yes or no), history of CB (Has the subject had bronchitis or chronic coughing with phlegm or sputum from the chest, for at least past 2 years, and at least 3 months in past year), Diabetes (yes-no), Gastroesophageal Reflux and remove (some of) aforementioned covariate(s) or add other covariate(s) if need.
- The data set will be randomly participated into training dataset (approximate two thirds of the full sample size, adjusted if necessary) and testing dataset (approximate one third of the full sample size, adjusted if necessary).
- The training dataset is used to fit the model using the predictors significant in the univariate model ( $P < 0.05$ , the criteria can be adjusted if necessary).
- The testing dataset is used to evaluate the performance of the fitted model where the C-index will be calculated, the predictors of the testing dataset will be same as those of training dataset.

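### The RAP amendment 2 logistic models for 18-month exacerbation give no rule for participants who leave before Month 18 without an event

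*SAP*

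**What the plan says.** The SAP file holds SAP amendment 3, followed by RAP amendment 2. The logistic models are in RAP section 7.4.1, and the version history shows that they were added at RAP amendment 2. The model is given as "Logistic regression with binary endpoint", and it has three responses. The main one for this point, listed third, is "moderate or severe exacerbation vs exacerbation free for 18 months in the full population". The one listed first uses the same comparison group but takes only moderate events as cases. The remaining one sets participants who had a severe event against all others, including those whose events were no worse than moderate.

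The third response is used again for four smaller covariate sets, and the sub-cohort model takes its responses from the full-population case. RAP section 4 defines the population without any follow-up requirement: "The Full Population will consist of all subjects who are enrolled in the study and attend Visit 1". RAP Appendix 5 keeps data collected before a participant is lost. RAP Appendix 6 names multiple imputation only for the MMRM. The sensitivity analyses listed for the logistic models change only how variables are selected.

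SAP amendment 3 section 7.1 has no logistic model. It analyses exacerbations by negative binomial regression with log time on study as offset. SAP section 2.1, on changes to the planned analyses, does not say that the logistic models are withdrawn. Table 1 in SAP section 3.1 still lists an exacerbation analysis at Month 18.

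**The concern.** A participant who leaves at month 9 after an exacerbation is a case. One who leaves at month 9 without an exacerbation is not a case and has not been observed event-free for 18 months. Applied literally, the two classes keep early leavers with events and drop early leavers without, so membership of the analysis set depends on the outcome. Two programmers could reasonably code the second group differently. The RAP allows for unequal follow-up elsewhere: its exacerbation rate model has a log-time offset, and its CID analysis includes a time-to-event model. The logistic models have neither.

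These are the multivariable exacerbation prediction models in the plan for which a C-index is reported, and they bear on the objective of testing whether Western predictors apply in China. An error here would affect the 18-month risks, the univariate P<0.05 screen, the coefficients and the C-index.

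**Working it through.** **Plan's own figure.** Protocol section 10.1.3 is the only source of a dropout rate: "Under the above assumptions with 95% confidence and a 25% drop out". With a within-subject SD of 233 mL, a slope term of 3.8 mL/year, P = 4 and D = 2.5:

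- sigma_p = sqrt(3.8² + 12×3×233²/(2.5²×4×5)) = 125.1, as stated.
- N per group = 1.96² × 125.1² × 2/15² = 534, against the stated 525. At 525 the half-width is 15.1 mL/year, so the figure agrees to rounding.
- 525/0.75 = 700, as stated.

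The 25% is therefore a planning allowance for completing FEV1 follow-up over 30 months. The documents give no expected exacerbation rate, so every rate below is an assumption.

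**Leaving before Month 18.** With a constant leaving rate, mu = -ln(0.75)/2.5 = 0.115 per year and 1 - 0.75^(18/30) = 15.9%. With linear dropout, 0.25 × 18/30 = 15.0%.

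**Leaving before Month 18 without an event.** For a constant event rate L per year, the share is mu/(mu+L) × [1 - exp(-1.5(mu+L))]:

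| L per year | 0 | 0.1 | 0.2 | 0.3 | 0.5 | 0.8 | 1.0 |
|---|---|---|---|---|---|---|---|
| Share | 15.9% | 14.8% | 13.8% | 12.8% | 11.3% | 9.4% | 8.4% |

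Linear dropout gives values about 0.6 to 1 point lower. The share is larger for the severe-exacerbation response, because a leaver with only a moderate event is unresolved there too.

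**Effect on risk and odds ratio.** Illustrative assumptions: GOLD I 0.3 per year, GOLD IV 0.9 per year, and gamma variation between participants with dispersion 1, so that event-free survival is 1/(1+Lt).

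- True 18-month risk: 0.45/1.45 = 31.0% (GOLD I) and 1.35/2.35 = 57.4% (GOLD IV).
- True odds ratio: 1.35/0.45 = 3.00.

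Let E be the probability of an event before leaving, the integral from 0 to 1.5 of L/(1+Lt)² × exp(-mu t). Let F = exp(-1.5mu)/(1+1.5L) be the probability of being followed to Month 18 event-free. The remainder, 1 - E - F, is unclassified. Coding leavers event-free reports risk E. Excluding them reports E/(E+F).

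With 25% dropout in both grades:

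| | E | Unclassified | F | Coded free | Excluded | True |
|---|---|---|---|---|---|---|
| GOLD I | 28.8% | 13.2% | 58.0% | 28.8% | 33.2% | 31.0% |
| GOLD IV | 54.0% | 10.2% | 35.8% | 54.0% | 60.1% | 57.4% |

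Odds ratios for IV vs I, from unrounded values:

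| 30-month dropout, GOLD I vs IV | Coded free | Excluded |
|---|---|---|
| 25% vs 25% | 2.91 (-3%) | 3.04 (+1%) |
| 20% vs 30% | 2.75 (-8%) | 3.19 (+6%) |
| 15% vs 45% | 2.43 (-19%) | 3.59 (+20%) |

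Without variation between participants, the same rates give a true odds ratio of 5.03. With equal dropout it reads 4.49 (-11%) coded free and 5.09 (+1%) excluded. For a predictor with no effect (0.5 per year in both groups, dispersion 1), the odds ratio stays at 1.00 under equal dropout. At 15% vs 45% it reads 0.85 coded free or 1.17 excluded, which could feed the P<0.05 screen.

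**The case against.** The case against making much of this has four parts.

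1. **The current plan's exacerbation model is unaffected.** This stands. The negative binomial model with offset in SAP section 7.1 allows for unequal follow-up. A reader might infer that the main exacerbation-rate results are compromised, but the documents do not support that. The point is limited to the RAP models, which SAP amendment 3 leaves unmentioned.
2. **Odds ratios are robust to the omission.** This largely stands when dropout is unrelated to the predictor. A reader might infer that odds ratios are biased whichever way leavers are coded. The calculation contradicts that: exclusion, which is the natural reading of the two classes, costs about 1%. Restricting the analysis to participants followed to Month 18 would cost nothing if leaving is independent of outcome given the covariates. Material bias needs dropout to differ by predictor. That is plausible for GOLD grade, CAT or age, but the documents do not show it.
3. **The share lost may be small.** This partly stands. Exacerbations are also collected by phone every three months, with hospital records checked where possible. Protocol section 8.3 counts a participant as lost only if unreachable and absent at both Visit 3 and Visit 4. Missing the Month 18 visit alone does not remove the outcome. A narrower figure such as 10-13% would need rates of about 0.28 to 0.69 per year, which the documents do not give.
4. **A Cox model changes the estimand.** This is true, and it is a cost of that option. Censoring weights avoid it.

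The objection does not dispose of the selection on outcome. Absolute risks are off by about 3 points in either direction even with equal dropout, and the handling rule is missing.

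**Conclusion.** The gap is real and limited in scope. The RAP amendment 2 logistic models define no outcome for participants who leave before Month 18 without an event. On the planning allowance that is roughly 8-16% of participants for assumed rates of 0 to 1 per year, possibly fewer because of the phone calls. Absolute 18-month risk is overstated if they are dropped and understated if they are coded event-free: 60% or 54% against 57% in the example. Odds ratios are little affected under equal dropout, and are pulled in opposite directions if dropout differs by predictor. These sizes rest on assumed exacerbation rates, an assumed spread of dropout over time and assumed dropout contrasts. Only the 25% allowance comes from the documents. The missing class for severe-only participants in the moderate-exacerbation response is a matter of clarification.

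**What to change.** For any reported use of these models, choose one of the following:

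- **Time to event.** Fit a Cox model for time to first moderate/severe exacerbation, and another for first severe exacerbation. Use the same predictors and the same training/testing split, censor at the last exacerbation enquiry or Month 18, and report Harrell's C.
- **Binary outcome.** Keep the logistic model and weight by the inverse probability of remaining under follow-up to Month 18.

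Both options assume that leaving is unrelated to later exacerbation, given the covariates used. If the models will not be reported, add a sentence to SAP section 2.1 saying that they are withdrawn in favour of the negative binomial model with offset. If the moderate-exacerbation response is kept, state that severe-only participants are excluded from it.

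The cost is SAP wording and some reprogramming, with no new data. The Cox option reports hazard ratios instead of 18-month odds ratios.

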### 13.2. Endotypes

Summary of endotypes in Sub-cohort Population will be provided totally and by (baseline) GOLD grades, including Airflow limitation blood eosinophils and plasma fibrinogen.

- Airflow limitation is defined as GOLD grade increased from baseline, and will be summarized by Yes (GOLD grade increased) and No (GOLD grade remain stable or decreased)
- Blood Eosinophils will be summarized by  $> 300 / \mu\text{l}$  and  $\leq 300 / \mu\text{l}$
- Plasma Fibrinogen will be summarized by  $> 400 \text{ mg/dl}$  and  $\leq 400 \text{ mg/dl}$

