
 
• Logistic regression with binary endpoint
 
• Response variable: Refer to the full population case
 
• Predictors/ covariates 
 
• Continuous variables: all continuous variables in full population case and LAA950, pi10, Steps walked within first week, DPM functional small airway disease, DPM tissue destruction, RV/TLC ratio and remove (some of) aforementioned sub cohort covariate(s) or add other sub cohort continuous variables if necessary.
 
• Categorical variables: all categorical variables in full population case and other sub cohort categorical variables if necessary
 
 
 
• All the sub cohort data will be used for model fitting, i.e., the training dataset is sub cohort data where the predictors are those are significant in the univariate model (P<0.05, relaxed to 0.1 if necessary).
 
• Create testing data by bootstrap method, i.e., resampling method with replacement, where the sample size of testing dataset is same as the sub cohort training dataset. The boot strap time is set to be 100, adjusted if necessary. For each bootstrap procedure, seed is required to set. For each testing dataset, the first type of C-index will be calculated based on the (same) model trained using the sub cohort data. The second type of C-index will be calculated based on the (same) model trained using the training dataset of the full population of the previous full population analysis section.
 
• The final two types of C-indexes derived based on the testing datasets will be present as the means and 95%CIs of the C-indexes based on the 100 bootstrap testing datasets.
 

Model Results Presentation

 
• For multivariate logistic regression model, fitted Statistics (-2 Log Likelihood, AIC, BIC, r square), regression coefficient, 95% confidence intervals of the regression coefficient, P value, C-index (Concordance index), will be presented based on the training dataset.
 
• The means and 95%CIs of the two types of C-indexes based on the 100 bootstrap testing datasets will be reported separately.
 
• Other Statistics will be reported if applicable.
 

Sensitivity Analyses

 
• Two multivariate logistic regression models will be built based on AIC stepwise, BIC stepwise criteria to be compared.
 

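### In the appended RAP's 18-month exacerbation prediction models, the CRP coding (low ≤3, high >30) leaves values above 3 and up to 30 without a level

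*SAP*

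**What the plan says.** RAP amendment 2, appended to the SAP, adds logistic prediction models for exacerbation over 18 months in section 7.4.1. The full-population specification lists continuous and categorical predictors. CRP is categorical: "CRP (low $\leq 3$ , high $> 30". Three other laboratory variables in the same list are also split in two:

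- "Neutrophil/lymphocyte ratio (low $< 5$ , high $\geq 5"
- "Eosinophils (low $< 300$ , high $\geq 300"
- "Fibrinogen (low $< 400$ high $\geq 400"

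Household income is split at 80000, with that value on the low side.

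The main model is fitted to a "training dataset (approximate two thirds of the full sample size, adjusted if necessary". Its entry rule is univariate significance: "The training dataset is used to fit the model using the predictors significant in the univariate model", at P<0.05 unless adjusted. The sensitivity analyses fit AIC and BIC stepwise models that offer every listed predictor and use the same training and testing sets. For the sub-cohort, the categorical predictors are "all categorical variables in full population case and other sub cohort categorical variables if necessary".

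The demo programs use PROC LOGISTIC and PROC HPLOGISTIC and show no option for keeping records with a missing predictor. The missing-data appendix names imputation only for the MMRM.

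**The concern.** A two-level predictor has to place every measured value in one level or the other. A CRP of 8 is neither low nor high under this rule, and nothing else in the protocol, SAP or RAP says where it belongs. A programmer must choose between leaving it missing, folding it into one of the two levels, or adding a third. Each choice gives a different model.

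Leaving it missing does the most damage, because complete-case fitting then selects the sample on the value of a predictor. The coefficients, fit statistics and C-indexes would describe participants whose CRP is ≤3 or >30, and would be reported as results for the full population or the sub-cohort. A test-set participant in the gap would also get no prediction from a model that contains CRP.

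**Working it through.** The plan states no sample size or precision for these models, so there is no figure to reproduce. The check has three parts.

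**1. Does the coding cover the scale?** Each rule was tested on a grid from 0 to 100 in steps of 0.1.

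| Rule | Values with no level |
|---|---|
| CRP ≤3 / >30 (as written) | 3.1 to 30.0 |
| CRP ≤3 / >3 | none |
| CRP ≤30 / >30 | none |
| Neutrophil/lymphocyte ratio <5 / ≥5 | none |

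Income, eosinophils (300) and fibrinogen (400) have the same number on both sides, so they leave no gap either.

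**2. Where would the gap act, if it is left missing?**

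- *Univariate CRP screen:* it uses only ≤3 and >30.
- *Main model:* affected only if CRP passes the screen.
- *AIC/BIC stepwise models:* CRP is always on the candidate list. By default, a record missing any candidate is dropped, whether or not CRP is finally selected.
- *Sub-cohort models and bootstrap C-indexes:* the coding is inherited.
- *Four covariate-set models* for moderate or severe exacerbation: CRP is not listed, so there is no effect unless it is added.
- *SAP 7.1 negative binomial model:* no CRP term, no effect.
- *SAP section 10 hsCRP summaries:* measured scale with geometric means, no effect.

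**3. How many participants?** The documents give neither a CRP distribution nor a unit, so everything here is assumption. Take hsCRP in mg/L as lognormal with median m and log-SD s:

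share in gap = Φ((ln 30 − ln m)/s) − Φ((ln 3 − ln m)/s)

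For m = 1.5 and s = 1.0 this is Φ(2.996) − Φ(0.693) = 0.9986 − 0.7559 = 24.3%.

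| m | s | Share >3 to ≤30 | Share >30 |
|---|---|---|---|
| 1 | 1.0 | 13.6% | 0.03% |
| 1 | 1.2 | 17.8% | 0.2% |
| 1.5 | 1.0 | 24.3% | 0.1% |
| 1.5 | 1.2 | 27.5% | 0.6% |
| 3 | 1.0 | 48.9% | 1.1% |
| 3 | 1.2 | 47.2% | 2.8% |
| 4 | 1.0 | 59.1% | 2.2% |
| 4 | 1.2 | 54.8% | 4.7% |

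A simpler conversion makes no distributional assumption: records lost = N × share in the gap. With 2,000 planned participants, the training set is 2,000 × 2/3 ≈ 1,333 and the test set about 667. The sub-cohort is 400.

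| Assumed share in gap | Training (1,333) | Test (667) | Sub-cohort (400) |
|---|---|---|---|
| 5% | 67 | 33 | 20 |
| 10% | 133 | 67 | 40 |
| 20% | 267 | 133 | 80 |
| 30% | 400 | 200 | 120 |
| 40% | 533 | 267 | 160 |

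These counts take all planned participants as the base. With the 1,700 planned COPD participants only, the training set is 1,700 × 2/3 ≈ 1,133 and the losses shrink in proportion.

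**The case against.** The strongest reply is that this is a typing slip, 3 against 30, or an omitted middle level. The complementary cut-offs beside it support that. No derivation of the CRP variable appears anywhere; the demo programs use placeholders for the predictors. Deletion follows only if the programmer sets the gap to missing and keeps the software default. The RAP also lets covariates be removed, so CRP may not stay in the models. All of this stands, and it is why the loss is stated conditionally. It does not settle the coding, because the text still cannot be programmed without an unrecorded choice.

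The second reply concerns reach. The affected models sit in the appended RAP; the body of SAP amendment 3 does not repeat them. This also stands, and it limits the importance of the point.

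Some stronger readings are tempting but not supported:

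- *The hsCRP endpoint itself is compromised.* It is not; SAP section 10 summarises it on its measured scale.
- *The univariate-screen model and the stepwise models would be compared on different patients.* The RAP is most naturally read as comparing the AIC model with the BIC model. Those two share a candidate list and data, so the CRP coding cannot separate their samples.
- *Participants in the gap carry most of the CRP information, or the group above 30 is certain to be tiny.* The documents contain no CRP data to show either.
- *The intended cut-off was 3.* Nothing in the documents decides between 3 and 30.

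**Conclusion.** The coding rule is wrong as written: it cannot classify every participant, and no other text closes the gap. That part rests on the wording alone. The loss of participants is an inference from two conditions: the gap is left missing, and the default complete-case handling of the logistic procedures applies. Its size is unknown. The 14% to 59% range rests on an assumed lognormal distribution in mg/L with median 1 to 4 and log-SD 1.0 to 1.2. The effect is confined to the 18-month logistic models of the appended RAP that use the full predictor list, and to the sub-cohort models that inherit it. It should be corrected before those models are run or relied on, but it does not touch the rest of the exacerbation or biomarker analyses.

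A trivial side point: the RAP model list puts exactly 300 eosinophils and exactly 400 fibrinogen in the high group. SAP 13.2 ("Plasma Fibrinogen will be summarized by" for fibrinogen, and likewise for eosinophils) uses a strict inequality, so those exact values count as not high. Only participants exactly at the cut-off are affected.

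**What to change.** - Make the CRP coding exhaustive. The sponsor should confirm one shared cut-off and state its unit. Alternatively, enter log(hsCRP) as a continuous predictor, which avoids the choice.
- State how records with a missing predictor are handled in the logistic models.
- If the models were run with the gap, rerun the univariate screen, the main and AIC/BIC models, and the training, testing and bootstrap C-indexes for the full population and the sub-cohort. Report the number of participants used in each fit.
- Use the same inequality at 300 and 400 in the RAP model list and SAP 13.2.

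The cost is a line or two of text and, if needed, a rerun of existing programs. No new data are required.

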### **9.2.9. Biomarker(s)**

#### **9.2.9.1. Blood biomarkers**

Blood samples will be taken at Visit 1 and throughout the study as defined in the Time and Events Table. ([Table 1](#))

- Plasma fibrinogen, hsCRP, total/differential blood cell count measurements and haemoglobin will be conducted at central lab for all participants
- Additional protein analysis will be conducted at central lab for the sub-cohort using validated assays. Analytes chosen will include serum sRAGE, CC16 and IP-10, HbA1c.

The blood biomarker assessments will be conducted according to the study reference manual.

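### The RAP's 18-month exacerbation models enter neutrophil/lymphocyte ratio, eosinophils and fibrinogen only as low/high splits, losing at least about 36% of a marker's information if its effect is roughly linear; the CRP split also leaves a gap

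*SAP*

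**What the plan says.** The models concerned are the logistic regressions for exacerbation in 18 months in RAP section 7.4.1 (RAP amendment 2, contained in the SAP document), for the full population and the sub-cohort.

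- Protocol 9.2.9.1 provides measured values: "Plasma fibrinogen, hsCRP, total/differential blood cell count measurements and haemoglobin will be conducted at central lab for all participants".
- The RAP lists age, pack-years, SGRQ, FEV1 and FVC % predicted, mMRC, CAT and haemoglobin as continuous predictors.
- Two inflammatory markers are listed as categorical: "Neutrophil/lymphocyte ratio (low $< 5$ , high $\geq 5$ ), Eosinophils (low $< 300$ , high $\geq 300".
- So is a third: "Fibrinogen (low $< 400$ high $\geq 400".
- CRP is in the same list: "CRP (low $\leq 3$ , high $> 30".
- For entry to the main multivariable model: "The training dataset is used to fit the model using the predictors significant in the univariate model". The level is P<0.05, but "the criteria can be adjusted if necessary", and covariates may be added or removed.
- The sensitivity analyses run AIC and BIC stepwise selection from all listed predictors, with the same coding.
- The sub-cohort model takes over "all categorical variables in full population case and other sub cohort categorical variables if necessary". Its screen may be relaxed to 0.1.

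The RAP gives no reason for the cuts, no share of participants above them and no expected 18-month event share.

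**The concern.** A single split treats values just either side of the cut as different and all values beyond it as equal. When risk changes smoothly with the marker, that discards information the laboratory has already supplied. Putting a significance screen after the split makes it more likely that a modest predictor never reaches the main model.

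The first research question asks whether predictors of progression found in Western cohorts apply in China. Protocol 5.4 presents fibrinogen as a promising marker linked to exacerbation, and blood eosinophils as marking a distinct exacerbation phenotype. For these markers, absence from the model could reflect the coding and not the biology.

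**Working it through.** The documents give no power, event count or information figure for these models, so there is no stated figure to reproduce.

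**Inputs from the documents.** The planned sample is 2,000, of whom 1,700 have COPD (RAP 5.1). The training share is about two thirds (RAP 7.4.1). There are 1,275 COPD completers after 25% dropout (Protocol 10.1.3). Training set: 1,700 × 2/3 ≈ 1,133; range 1,275 × 2/3 = 850 to 2,000 × 2/3 ≈ 1,333.

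**Inputs assumed, because the documents do not give them.** Share above the cut p, 5% to 50%. Event share q, 10% to 40%. Odds ratio per SD of the log marker, 1.15 to 1.5.

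**Step 1: information kept.** For a marker that is normal on the log scale with linear log-odds, a split keeps RE = φ(z_p)² / [p(1−p)], where z_p is the normal quantile at the cut. At p = 20%, z_p = 0.842 and φ = 0.280, so RE = 0.0784/0.16 = 0.49. The best case is p = 50%: RE = 0.1592/0.25 = 0.637, a loss of 36%. The loss reaches half at p ≈ 21% (or, by symmetry, 79%).

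**Step 2: chance of passing P<0.05.** Power = Φ(ln OR × √[n q(1−q) RE] − 1.96). With n = 1,133, q = 0.30 and OR = 1.2, the continuous marker gives 0.1823 × √237.9 = 2.81, so Φ(0.85) ≈ 80%. With the split:

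| Share above cut | Information lost | Chance of passing |
|---|---|---|
| (continuous) | 0% | 80% |
| 50% | 36% | 61% |
| 30% | 42% | 57% |
| 20% | 51% | 50% |
| 10% | 66% | 38% |
| 5% | 78% | 27% |

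**Step 3: other assumptions.**

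- n = 850, q = 30%, OR 1.2: 68% continuous; 49% down to 21% split.
- n = 1,333, q = 40%, OR 1.2: 90% continuous; 74% down to 34% split.
- n = 850, q = 10%, OR 1.2 (a rarer outcome): 36% continuous; 25% down to 12% split.
- n = 1,133, q = 30%, OR 1.5: about 100% continuous; 100%, 99%, 96% and 84% split at p = 50%, 20%, 10% and 5%.
- All 400 sub-cohort participants, q = 30%, OR 1.2: 39% continuous; 27% down to 12% split.

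**Step 4: check by simulation** (4,000 replicates, n = 1,133, q = 30%, OR 1.2 per SD).

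| True shape | Continuous | Split |
|---|---|---|
| Linear, normal marker | 79–80% | 60% down to 30% |
| Linear on the raw scale, skewed marker | 81–84% | 50–61% |
| Step exactly at the cut | 33–61% | 79–85% |

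**Step 5: CRP.** This needs no assumption. Low ends at 3 and high starts above 30, so a value such as 10 belongs to neither level. The documents do not say whether 30 is a slip or how such values are to be handled.

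**The case against.** Several points on the other side are sound.

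- Two cuts correspond to the plan's own endotypes. SAP 13.2 summarises eosinophils above 300 and fibrinogen above 400, and RAP 5.3.1 names endotypes as possible covariates. The cuts are pre-set, and whether an endotype predicts exacerbation is a fair question. This supports reporting the splits, but not making them the only coding. The match is also inexact: SAP 13.2 uses strictly above, while RAP 7.4.1 includes the cut value.
- If risk truly steps at the cut, the split is the better coding, as the simulation shows. The documents do not settle the shape, so the linear effect is an assumption. SAP section 10 does add geometric means for these markers, which suggests that a log scale is considered meaningful.
- A reader might infer that each marker must pass P<0.05 to be considered. It need not: the threshold and covariate list are adjustable, and the AIC and BIC models bypass the screen. They do not bypass the low/high coding, so the information loss remains.
- A reader might infer that half or more of every marker's information is lost. That needs extreme cuts for all three. At 25% to 50% above the cut the loss is 46% to 36%, and no section gives the shares.
- The study is stated to be mainly descriptive, without formal inference. Nothing says that an omitted marker will be reported as not predictive in China.

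**Conclusion.** The point holds as a coding weakness in exploratory models. Under a roughly linear log-scale effect, each split loses at least about 36% of the marker's information, and more than half only if about 21% or fewer (or 79% or more) exceed the cut. In the worked case, the chance that a real predictor is screened out rises from 20% to between 39% (half above the cut) and 73% (5% above).

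It would go too far to say that the splits will drop real predictors. Across the assumed ranges, the chance of missing one after the split runs from about 0% to about 91%, and a strong predictor usually survives. A loss of C-index is plausible but was not calculated.

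The scope is limited. The later four-set models in RAP 7.4.1 contain no blood markers, and SAP amendment 3 section 7.1 plans only a descriptive summary and a negative binomial model for exacerbations. The CRP gap is certain from the text. Overall this is a desirable improvement that threatens no main result.

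**What to change.** In the RAP 7.4.1 exacerbation models, full population and sub-cohort:

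1. Enter neutrophil/lymphocyte ratio, eosinophils, fibrinogen and CRP as continuous log-transformed values in the univariate, multivariable, AIC and BIC models. State in advance a small offset for zero eosinophil counts.
2. Check linearity of each marker on the log scale, for example with a spline.
3. Keep the 5, 300 and 400 cuts as a secondary endotype display, with one convention for values equal to the cut. Give CRP a cut that leaves no gap.

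With the screen unchanged, this restores the roughly 80% chance in the worked case. It costs RAP/SAP wording and recoding of existing data; if the models have been run, they need a re-run. Odds ratios per doubling or per SD are less familiar than low against high, and a spline uses extra degrees of freedom. If risk does step at a cut, the continuous term is the weaker coding, and the secondary display covers that case.
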